### 12.6. Safety Analyses

All safety analyses will be completed for the FAS. All safety data will be listed and summarized. No formal statistics will be performed for the safety analysis.

#### 12.6.1. Adverse Events

An AE is defined as any untoward medical occurrence associated with the use of a drug in humans, whether or not considered drug related.

TEAEs are defined as AEs with an onset date on or after the first administration of study medication and before the date of last administration of study medication + 14 days.

An SAE is defined as any AE that results in any of the following outcomes: death, a life-threatening AE, inpatient hospitalization or prolongation of existing hospitalization, a persistent or significant incapacity or substantial disruption of the ability to conduct normal activities of daily living, or a congenital anomaly/birth defect. Important medical events that may not result in death, be life-threatening, or require hospitalization may be considered SAEs when, based upon appropriate medical judgment, they may jeopardize the patient and may require medical or surgical intervention to prevent one of the outcomes listed in this definition.

The severity of AEs will be classified by the investigator as mild, moderate, or severe.

The causality of AEs will be classified by the investigator as related and not related.

An overall AE summary will be generated presenting the frequency and percentage of patients and the number of AEs using FAS for the following:

- Any TEAE
- Any treatment-related TEAE
- Any severe TEAE
- Any treatment-related severe TEAE
- Any SAE
- Any treatment-related SAE
- Any TEAE leading to study discontinuation
- Any death
- Any Suspected Unexpected Serious Adverse Reaction
- Any Adverse Events of Special Interest

All AEs will be coded using MedDRA (version to be delineated in the clinical study report [CSR]). The TEAEs will also be summarized by SOC, PT, by severity and relationship to study treatment. Missing or partial medication start/stop date will be imputed as described in [Appendix 3](#).

The TEAE summary tables will be sorted by SOC and PT. System organ class will be displayed in descending order of overall frequency then alphabetically. Preferred term will be displayed in descending order of overall frequency and then alphabetically within SOC. A patient with 2 or more events within the same level of summarization will be counted only once in that level using the most severe incident or most related incident. Percentages will be based on the number of patients in the FAS.

A TEAE summary table by prevalence will also be provided. The preferred terms will be sorted by decreasing frequency in the active arm.

All AEs will be presented in a data listing. Separate data listings will be generated for treatment related AEs, SAEs, and AEs leading to study discontinuation.

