 - New finding of QRS $>120 \text{ ms}$ (if not present at the Screening Visit. For example, patients with Right Bundle Branch Block at screening would not need to be withdrawn from the study if their subsequent ECGs remained unchanged).
 - Evidence of QT-interval prolongation, defined as an increase in the QTcF interval $>60 \text{ ms}$ from Visit 1.
 - Acute signs of ischemia or infarction.
 - Any ECG abnormality that may, in the opinion of the investigator, represent a new medical issue of concern.

In addition, patients should discontinue study medication if any of the following occurs:

1. The patient withdraws his/her consent to participate in the study.
2. The patient develops an illness that would interfere with his/her continued participation in the study.
3. The patient is noncompliant with study procedures or medication, in the opinion of the investigator.
4. The patient is confirmed to be pregnant.
5. The sponsor or regulatory agency requests withdrawal of the patient.

If a patient is prematurely discontinued from study medication, the patient may remain in the study. The patient should complete the assessments outlined for each study visit; see [Table 1](#). The patient should also attend the PTFU Visit.

Every effort will be made to ensure that patients who prematurely discontinue study medication complete the study.

Patients who discontinue study medication prematurely will not be replaced.

Patients are permitted to temporarily discontinue and restart study medication.

5.4.2 *Premature Discontinuation from the Study*

Participation in the study is strictly voluntary. A patient has the right to withdraw from the study at any time for any reason, without any reprisal.

At the time of premature study discontinuation, the investigator should make every effort to ensure the patient completes the assessments indicated at the Day 28/ET Visit and completes the PTFU Visit approximately 14 days after the ET Visit; see Table 1. The only exception to this requirement is when consent is withdrawn for all study procedures or the participant loses the ability to consent freely (e.g., is imprisoned or involuntarily incarcerated for the treatment of either a psychiatric or physical illness).

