Treatment group comparisons for categorical efficacy endpoints (IGA Response, EASI-50, EASI-75, and EASI-90) that are conducted over time will employ a logistic regression model fit at each scheduled visit separately, where appropriate. The logistic regression model will include treatment group as a factor and the baseline value and/or baseline severity of AD as a covariate. Model-based point estimates for the treatment proportions will be provided as well as model-based differences and corresponding 90% confidence intervals and 1-sided p-values.

9.4.6 *Analysis of Safety*

The FAS will be used for the analysis of safety data (AEs, clinical laboratory, vital signs, physical examination results, and ECGs).

AEs will be coded with MedDRA. TEAEs are defined as AEs with onset dates on or after the date of first administration of study medication through the end of the study, or that exist prior to the first dose and worsen with dosing. TEAEs will be presented by system organ class and preferred term in frequency tables. Patients with multiple AEs will be counted only once within each preferred term and system organ class. Key patient information for patients with an AE with an outcome of death, patients with SAEs, and patients with an AE leading to discontinuation of study medication will be listed.

Laboratory data (hematology, serum chemistry, and urinalysis) will be converted to Système International units for reporting and processing purposes. Absolute values and changes from baseline will be presented descriptively. Laboratory data outside study-specific reference ranges will be listed.

Vital signs and ECG parameters will be presented descriptively.

9.4.7 *Demographic and Baseline Characteristics*

Demographic characteristics (including age, sex, ethnicity, and race) and baseline characteristics (including height, weight, and disease characteristics) will be presented descriptively.

9.4.8 *Pharmacokinetic Endpoints*

Individual and mean plasma concentrations at each sampling time point for ATI-1777 will be listed and summarized in a tabular form including means, geometric means, ranges, standard deviations, and coefficients of variation. Mean concentrations will be plotted versus nominal time on linear and semilogarithmic scales.

9.4.9 *Handling of Missing Values*

Patients who discontinue study medication will be asked to come to each visit for the scheduled assessments up to the end of the study.

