## 10. Conventions and Derivations

Patients who discontinue study medication will be asked to come to each visit for the scheduled assessments up to the end of the study.

Patients who prematurely discontinue the study will be evaluated based on the data collected at each visit attended. Data collected during the ET Visit will be used as an end-of-study assessment for these patients. If the ET Visit was performed >1 day after the last dose was administered, then the previous visit will be used as the end-of-study assessment.

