### 12.1. Patient Disposition

#### 12.1.1. Disposition

The number of patients screened, randomized, randomized and treated, randomized and not treated, and the number of patients in the analysis sets will be summarized for all screened patients.

The number and percentage of patients will also be summarized for the following patient disposition categories:

1. Completed study drug treatment PP
2. Discontinued study drug early and the reason for discontinuation
3. Completed the study including PTFU
4. Discontinued from the study early and the reason for discontinuation

The table will be presented by treatment arm using the FAS.

All patient's disposition data will be listed.

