#### 12.4.3.3. Imputation for Intercurrent Events

An intercurrent event is one that occurs after the first dose of study medication and either precludes the observation of the primary variable/endpoint or affects its interpretation. The following is a list of intercurrent events that could occur during this study:

- Death
- Withdrawal from study
- Withdrawal of study medication due to an AE
- Rescue with a non-protocol specified treatment for AD

Missing data and data following these intercurrent events will be imputed using the LOCF methodology.

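### The SAP's adverse event outputs cover AEs leading to study discontinuation only, so the protocol's listing of AEs leading to discontinuation of study medication is not specified

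*SAP*

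**What the plan says.** Protocol Section 9.4.6 (Analysis of Safety) states that key information on "patients with an AE leading to discontinuation of study medication will be listed". The protocol summary carries the same requirement under its safety analyses.

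SAP Section 12.6.1 specifies two discontinuation outputs for AEs. The overall AE summary has the row "Any TEAE leading to study discontinuation". On listings it states: "Separate data listings will be generated for treatment related AEs, SAEs, and AEs leading to study discontinuation". Neither refers to stopping study medication.

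Both documents provide for patients who stop drug without leaving the study. Protocol Section 5.4.1 states: "If a patient is prematurely discontinued from study medication, the patient may remain in the study". SAP Section 10 states: "Patients who discontinue study medication will be asked to come to each visit for the scheduled assessments up to the end of the study".

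Outside the AE section, the disposition table in SAP Section 12.1.1 includes the category "Discontinued study drug early and the reason for discontinuation", by treatment arm, and all disposition data are to be listed.

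**The concern.** The protocol asks about one event and the SAP reports on another. A programmer who follows SAP Section 12.6.1 as written would not produce the protocol's listing. The one AE-discontinuation row in the overall summary would leave out anyone who came off drug because of an AE and then finished follow-up.

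Safety and tolerability are secondary objectives of this first-in-human study. The individual stopping rules in Protocol Section 4.4.1 act on treatment, and the periodic safety review in Section 4.4.2 pays particular attention to patients who meet them. A patient taken off treatment under those rules could stay in follow-up and then be absent from both AE-discontinuation outputs in the final report.

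**Working it through.** No figure in the plan is at issue, so the check is a comparison of texts, followed by one line of arithmetic for scale.

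**1. What is required and what is specified**

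| Output | Protocol 9.4.6 and summary | SAP 12.6.1 |
|---|---|---|
| Dedicated AE listing | AE leading to stopping study medication | AE leading to leaving the study |
| Row in overall AE summary | None required | AE leading to leaving the study |

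The listing is the direct departure from the protocol. The summary row has the same gap, but it does not breach a protocol requirement.

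**2. Is this only loose wording?** The SAP could be using study discontinuation as shorthand for stopping study drug. Its other sections make that hard to sustain:

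- Section 12.1.1 has separate disposition categories for stopping drug early and for leaving the study early.
- Section 12.4.3.3 lists "Withdrawal of study medication due to an AE" as an intercurrent event of its own, apart from withdrawal from the study.
- Section 10 asks patients who have stopped drug to keep attending visits.
- SAP Appendix 1, like Protocol Appendix 4, allows a participant permanently taken off treatment to continue in the study for follow-up assessments.

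The SAP therefore treats the two as different events, and its AE outputs name only one of them.

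**3. Is the departure declared?** SAP Section 6.1 records changes to the sample size computation, the scope of LOCF and the severity covariate. It does not mention AE listings.

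**4. Who is left out?** Take a patient who stops drug for an AE, attends the remaining visits and completes the study. That patient counts 0 in the SAP summary row and 0 in the SAP dedicated listing, and would be in the protocol's listing.

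**5. Where would that patient still be seen?** In the disposition table, under early drug discontinuation and its reason; in the disposition listing; and in the listing of all AEs. None of these is specified to show which AE led to the drug stop, or that AE's severity and relatedness.

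**6. Scale.** Allocation is 1:1.

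- Protocol: about 50 patients, 50/2 = 25 per arm, and 1/25 = 4.0 percentage points per patient.
- SAP: about 42 patients, 42/2 = 21 per arm, and 1/21 = 4.8 percentage points per patient.

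Neither document gives an expected rate of AE-driven drug stops, so no expected number omitted can be calculated.

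**The case against.** The strongest reply is that little is lost. If adverse event is a coded reason for stopping drug, the disposition table already gives the count per arm and the disposition listing identifies the patients. The eCRF is not available, so that coding is an assumption. This part stands: a reader might infer that AE-driven drug stops disappear from the report, and the documents do not support that. What remains missing is the dedicated listing and the link to the specific event.

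A second reply is that the documents do not separate the two events cleanly. Protocol Section 4.1.2 gives patients who stop drug before Day 28 an Early Termination Visit at that time and then the post-treatment visit. Sections 5.4.1 and 9.4.9 have them continue with scheduled visits. The ECG findings listed in Section 5.4.1 lead to withdrawal from the study as well as from drug. This also stands in part: some AE-driven stops would appear in the SAP's row, and how many depends on how these sections are reconciled. A reader might infer that the row will read zero whatever the true rate. That would be so only if every such patient completed the study, and the ECG provision alone rules it out as a general statement.

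A third reply is that discontinuation for an AE is not a named endpoint. That is correct. A reader might infer that the study's main tolerability measure is lost, but the safety endpoints are TEAEs and SAEs, laboratory values, vital signs, physical examination and ECG. AESIs, including application site AEs, have their own summary in SAP Section 12.6.1.2.

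Finally, the SAP was written against protocol V2.0 and the protocol supplied is Version 4. The change entries that can be read do not touch this requirement, but the V2.0 wording cannot be confirmed. That may explain the mismatch. It does not remove it, because SAP Section 6 itself expects protocol changes to prompt SAP updates where needed.

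**Conclusion.** The conflict holds. As written, SAP Section 12.6.1 does not produce the listing that Protocol Section 9.4.6 requires, and the departure is not recorded in Section 6.1. The overall AE summary has the same gap.

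The consequence is limited to these two AE outputs. A patient who stops drug for an AE and completes follow-up is absent from both, at 4.0 to 4.8 percentage points of an arm for each such patient, but can still be traced through disposition and the full AE listing. The conclusion assumes that study discontinuation means in Section 12.6.1 what it means in Section 12.1.1, and that at least some patients who stop drug for an AE remain in the study. It should be corrected before database lock, but it does not affect the efficacy analysis or the collection of safety data.

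**What to change.** In SAP Section 12.6.1:

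1. Add a listing of AEs leading to discontinuation of study medication, with preferred term, severity and relatedness. The protocol requires the listing; naming these columns supplies the missing link to the event.
2. Add a matching row for TEAEs leading to discontinuation of study medication to the overall AE summary.
3. Keep the existing row and listing for study discontinuation.

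If the sponsor prefers not to produce the listing, record and justify the departure in SAP Section 6.1.

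A row for AEs leading to interruption of study medication is optional. Protocol Section 7.4.2 has interruptions and their reasons recorded in the eCRF, but neither document asks for AEs to be tabulated that way.

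The cost is one listing and one table row. Before programming, confirm that the eCRF ties each drug stop to the responsible AE; the documents do not show this.

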### **12.6.1.1. Suspected Unexpected Serious Adverse Reaction**

A suspected unexpected serious adverse reaction (SUSAR) is defined as any AE for which there is a reasonable possibility that the study medication caused the AE (where 'reasonable possibility' means there is evidence to suggest a causal relationship between the study medication and the AE), the AE is not listed in the Investigator Brochure (IB) or is not listed at the specificity or severity that has been observed, and the AE meets at least one of the criteria for seriousness.

The SUSAR will be summarized by SOC and PT. The SUSAR will also be presented in a data listing.

### **12.6.1.2. Adverse Events of Special Interest**

The adverse events of special interest (AESIs) for this study are TEAEs of:

- Application site AEs
- Serious infections
- Malignancies
- Thrombosis

- Cytopenias
- Liver enzyme elevation AEs (e.g., ALT, AST, bilirubin, GGT, LDH)
- Increased lipid parameter AEs (e.g., TC, LDL-C, HDL-C, TG)

The AESI will be summarized by SOC and PT. The AESI will also be presented in a data listing.

### 12.6.2. Laboratory Data

Laboratory parameters will be summarized for FAS. Laboratory data (hematology, serum chemistry, and urinalysis) will be converted to Système International units for reporting and processing purposes. Summaries by visit will include data from scheduled assessments, and all data will be reported according to the visit window for which it was recorded. Absolute values and changes from baseline will be presented descriptively.

Hematology, serum chemistry, and urinalysis will be summarized using descriptive statistics for numeric variables and numbers and percentages for categorical variables at each scheduled assessment. Numeric hematology, chemistry, and urinalysis results will be summarized using change from baseline as well. Where it is applicable to categorize a laboratory assessment by normal, high, or low according to the normal range provided by the central laboratory, the status at the final value at the end of the treatment period will be compared with that at the study baseline and the "shifts" from study baseline will be summarized using the number and percentage of patients in each shift category by treatment group.

All clinical laboratory test results will be presented in the data listings. Laboratory values that are outside of the normal reference range will be flagged in the data listings.

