1.3.2.5 Cytopenias

Cytopenias (lymphopenia, neutropenia, anemia, and thrombocytopenia) have been reported after chronic oral dosing with commercially available JAK1/JAK2 and pan-JAK inhibitors such as ruxolitinib, upadacitinib, and tofacitinib. Treatment with ATI-1777 should be avoided in patients with cytopenias. Patients with laboratory values indicative of cytopenias will be excluded from the study. Cytopenias will be monitored during the study and reported as AEs.

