7.4.2 Dose Modification

Study medication dosing for individual patients will be allowed to be paused and restarted if it is deemed to be in the best interest of the patient's safety due to AE. Decisions regarding dose interruptions or modifications will be made by the investigator in consultation with the medical monitor based on the clinical evaluation of the patient. All treatment interruptions and the reason for the interruption should be recorded in the eCRF.

Treatment with ATI-1777 should be temporarily interrupted in the event of severe AEs considered related to ATI-1777, or in the event of one or more of the abnormal laboratory values in Table 5.

Table 5 Study Medication Interruption Criteria

Laboratory Test	Hold Study Medication if:	Resume Study Medication if:
WBC count	$<2 \times 10^9/L$	$\geq 2.5 \times 10^9/L$
ANC	$<1 \times 10^9/L$	$\geq 1.5 \times 10^9/L$
Lymphocyte count	$<0.5 \times 10^9/L$	$\geq 0.75 \times 10^9/L$
Platelet count	$<75 \times 10^9/L$	$\geq 100 \times 10^9/L$
Hemoglobin	8 g/dL or a decrease >2 g/dL	≥ 10 g/dL
AST or ALT	$>3 \times ULN$	$<2 \times ULN$ or within 20% of baseline values
Serum creatinine	$>2 \times ULN$	$<1.5 \times ULN$ or within 10% of baseline value

ALT = alanine aminotransferase; ANC = absolute neutrophil count; AST = aspartate aminotransferase; ULN = upper limit of normal range; WBC = white blood cell

If a patient has one or more of the abnormal laboratory values noted in [Table 5](#), the investigator or designee upon receipt and review of the central laboratory report should instruct the patient to hold study medication applications. The investigator or designee should ask the patient about symptoms, concomitant illnesses and medications and repeat the test(s) as soon as possible. The medical monitor must be notified of dose interruptions due to AEs or laboratory abnormalities noted in Table 5.

If the retest confirms the abnormal laboratory value, then the study medication should continue to be held followed by repeat testing once a week or sooner at the discretion of the investigator. The patient should be followed until the laboratory abnormality(s) returns to normal or to baseline values.

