**Figure 1 Study Schematic**

**Table 1 Schedule of Events**

| Study Period  | Screening | Treatment Period |                  |                   |                      | PTFU              |
|---|-----------|------------------|------------------|-------------------|----------------------|-------------------|
| Study Day   | -30 to -1 | Day 1            | Day 8
±3 days | Day 15
±3 days | Day 28/ET
±2 days | Day 42
±3 days |
| Informed Consent    | X         |                  |                  |                   |                      |                   |
| Inclusion/Exclusion criteria  | X         | X                |                  |                   |                      |                   |
| Demographics  | X         |                  |                  |                   |                      |                   |
| Medical history, including AD history   | X         | X                |                  |                   |                      |                   |
| Full physical examination   | X         |                  |                  |                   |                      |                   |
| Brief physical examination    |           | X                |                  |                   |                      | X                 |
| SARS-CoV-2 nasopharyngeal test  |           | X                |                  |                   |                      |                   |
| ECG   | X         |                  |                  |                   |                      | X                 |
| Vital signs   | X         | X                | X                | X                 | X                    | X                 |
| Serum pregnancy test    | X         |                  |                  |                   |                      |                   |
| Urine pregnancy test  |           | X                | X                | X                 | X                    |                   |
| Clinical chemistry, hematology, urinalysis                          | X         | X                | X                | X                 | X                    |                   |
| Virology (Hepatitis B and C, HIV)   | X         |                  |                  |                   |                      |                   |

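### The only laboratory shift table uses the final treatment-period value, so abnormalities that resolve count as no shift, and no table counts patients who ever crossed a hold or discontinuation limit

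*SAP*

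**What the plan says.** SAP 12.6.2 (Laboratory Data) describes one shift analysis. It applies where it is possible to "categorize a laboratory assessment by normal, high, or low according to the normal range provided by the central laboratory", and "the status at the final value at the end of the treatment period will be compared with that at the study baseline". The section plans no shift by visit, no shift to the worst value, and no count of patients meeting a laboratory limit. For the by-visit tables it states: "Summaries by visit will include data from scheduled assessments".

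The row "Clinical chemistry, hematology, urinalysis" in the SAP schedule (Table 1) is marked at screening and on Days 1, 8, 15 and 28/ET. Day 1 samples are taken before dosing, so there are three scheduled post-baseline draws.

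Protocol 7.4.2 interrupts treatment for severe related AEs or "in the event of one or more of the abnormal laboratory values in Table 5". Table 5, repeated as SAP Appendix 2, covers WBC, ANC, lymphocytes, platelets, hemoglobin, AST/ALT and creatinine. If a retest confirms the abnormality, drug should "continue to be held followed by repeat testing once a week or sooner at the discretion of the investigator", and the patient is followed until the value is normal or back to baseline. Protocol 5.4.1 adds laboratory limits for permanent discontinuation. On cytopenias, protocol 1.3.2.5 states: "Cytopenias will be monitored during the study and reported as AEs".

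**The concern.** The protocol responds to a laboratory abnormality by stopping drug and waiting for recovery. A shift table that looks only at the last value measures patients after that response has had time to work. If ATI-1777 lowers counts or raises liver enzymes reversibly, the patients who were held and recovered are the ones the table records as unchanged. The error runs in one direction, toward no effect.

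This is a first-in-human study with safety as a secondary objective, and protocol 1.3.2 names cytopenias and liver-enzyme elevations as potential risks. A reader comparing the arms will naturally turn to the shift table, because it is the only planned categorical comparison by arm of laboratory values against a reference range. If it shows no shifts, it may be read as showing that no patient went out of range.

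**Working it through.** The plan gives no figure on this point to reproduce. The check applies the SAP rule to example patients and then asks which other outputs would show the same event.

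**Step 1. The rule on example paths.** Inputs from the documents: draws on Days 8, 15 and 28; AST/ALT hold limit >3 × ULN; resume limit <2 × ULN or within 20% of baseline (Table 5). The ALT paths are assumed, in multiples of ULN, and High means above 1.

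| Baseline, Day 8, Day 15, Day 28 | Final-value rule | Worst-value rule |
|---|---|---|
| 0.6, 3.5, 1.9, 0.9 | Normal to Normal | Normal to High |
| 0.6, 0.7, 3.4, 0.8 | Normal to Normal | Normal to High |
| 0.6, 3.5, 2.4, 1.8 | Normal to High | Normal to High |

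The first two patients crossed the hold limit and show no shift. The third fell below 2 × ULN but stayed above ULN, so both rules show a shift. The loss therefore needs a return to the baseline category; meeting the resume limit alone is not enough.

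**Step 2. How many patients could be missed.** Let n be patients per arm and p the assumed chance per patient of a hold-level event that normalises by the final value. Expected number missed = n × p. Chance of missing at least one in the arm = 1 − (1 − p)^n. The protocol plans about 50 patients (n = 25 per arm) and the SAP about 42 (n = 21).

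| p (assumed) | n = 25: expected; chance of at least one | n = 21: expected; chance of at least one |
|---|---|---|
| 2% | 0.5; 1 − 0.98^25 = 40% | 0.42; 1 − 0.98^21 = 35% |
| 5% | 1.25; 1 − 0.95^25 = 72% | 1.05; 1 − 0.95^21 = 66% |
| 10% | 2.5; 1 − 0.90^25 = 93% | 2.1; 1 − 0.90^21 = 89% |

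Neither document gives a value for p. As a single illustration, also assumed: if 3 of 25 ATI-1777 patients cross the ANC hold limit on Day 8 or 15 and are normal at the final value, the shift table shows 0/25 for them, where a worst-value table shows 3/25 = 12%.

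**Step 3. Where else the event appears.**

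- *AE tables.* Protocol 8.1.4 requires an AE for any laboratory abnormality that leads to interruption, modification or discontinuation of drug. SAP 12.6.1 tabulates TEAEs by SOC, PT, severity and relationship, and 12.6.1.2 tabulates AESIs, including cytopenias and liver-enzyme elevations. Creatinine is a hold parameter without an AESI category, so a creatinine hold would appear only among TEAEs in general.
- *By-visit summaries.* SAP section 12 includes minimum and maximum, so an extreme Day 8 or Day 15 value is visible. These show that an extreme value occurred, but not how many patients crossed a limit. They use scheduled assessments, and where several values fall in one window SAP 10.1.1 takes the one closest to the target day, so confirmatory and weekly repeats can drop out.
- *Listings.* All results are listed, with out-of-range values flagged.
- *Not covered.* No table counts by arm the patients whose values ever met a Table 5 or 5.4.1 limit. Out-of-range values that cause no hold and are judged not clinically significant are not AEs under 8.1.4, so they reach only the by-visit summaries and listings. A hemoglobin fall of more than 2 g/dL is a hold criterion but can stay inside the reference range; no normal/high/low shift would show it, whichever value is used.

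SAP 12.6.5, by contrast, plans QTcF categories (above 450, 480 and 500 ms; increases above 30 and 60 ms). The laboratory limits that govern holds and discontinuation have no such categories.

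**The case against.** The strongest reply is that the patients who matter most are already counted. Anyone whose drug was held or stopped for a laboratory value must be an AE case, and cytopenias and liver-enzyme rises have their own AESI tables with patient counts. In the illustration, the three patients with an ANC hold should appear as 3/25 in the AESI output. By-visit extremes and flagged listings add to this, safety output is descriptive, and the study is small enough for the listings to be read in full. A reader might infer from the shift rule that the safety analysis hides hold-triggering events, or that only mean changes and unsummarised listings remain. The documents do not support either inference, for the reasons just given.

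Two further limits stand. First, recovery enough to resume drug is not normalisation, as the third ALT path shows. Second, a patient who stops drug early need not be lost from the table. Protocol 4.1.2 places an ET visit at the time of discontinuation, laboratory samples are scheduled at Day 28/ET, and SAP section 10 uses ET data, or the previous visit if ET was more than 1 day after the last dose, as the end-of-study assessment for patients who leave the study. The final value may then be the abnormal one. Protocol 5.4.1 and 9.4.9 also ask patients off drug to keep attending, so a later normal value is possible too.

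The reply does not remove the gap. AE tables count reported terms, carry no numeric depth, and omit excursions that are neither acted on nor clinically significant. They do not show from the laboratory data how many patients in each arm crossed a stated limit.

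**Conclusion.** The point holds for the shift table and is of modest weight for the study. As written, SAP 12.6.2 counts as no shift any patient who returns to the baseline category by the final value, whatever happened on Day 8, on Day 15 or at an unscheduled retest. Two of the three scheduled post-baseline draws cannot affect the table unless one of them is the patient's last value. The bias is toward no laboratory effect.

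Its size depends on how often transient abnormalities occur, which the documents do not say. The 35% to 93% range above rests on assumed rates of 2% to 10% and on independence between patients. The 0% against 12% contrast describes one table under one assumption and should not be read as what the study would report overall. The conclusion does not extend to the AE and AESI analyses.

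**What to change.** In SAP 12.6.2:

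1. Add a shift table from baseline to the worst post-baseline value: lowest for hematology counts; highest for AST/ALT, bilirubin, creatinine and lipids. Include unscheduled and repeat samples. No laboratory draw is scheduled at Day 42 in SAP Table 1, so a period running beyond Day 28 would add only unscheduled samples.
2. Keep the final-value shift as a secondary table, since it shows status at the end of treatment.
3. Add one table by arm counting patients who ever met each existing Table 5/Appendix 2 hold limit and each existing protocol 5.4.1 laboratory discontinuation limit. This separates a hold-level event from a slight departure from the reference range, which a worst-value shift alone does not do. It also picks up the hemoglobin-fall criterion.

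The cost is SAP wording and one or two extra tables from data already collected. No clinical rule changes. Worst-value tables will show more chance excursions in both arms, and the vehicle arm gives the background rate against which to read them.
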